Variables:	
As stated above the patients will be grouped by type of treatment initiated or switched to. This will include Spiriva Respimat, a higher dose of ICS/LABA FDC, a new ICS/LABA FDC or an LTRA. Patient characteristics will be identified based on data recorded on the index date (date of dispensing/initiation of the exposure), or when a characteristic was not recorded on the index date, during the pre-index period (the one closest to the index date), unless otherwise specified.
 
The outcome is whether a patient has a cardiac arrhythmias diagnosis on the index date or in the year prior to the index date. The secondary outcome is whether a patient has a cardiac failure diagnosis on the index date or in the year prior to the index date.
 
In addition, the following covariates will be assessed in this study:
 
 • Demographic characteristics • Lifestyle factors • Asthma history and lab tests • Comorbidities • Concomitant prescriptions (both asthma related and non-asthma related prescriptions) 		
Data sources:	United Kingdom's Clinical Practice Research Datalink (CPRD) GOLD database		

Protocol for non-interventional studies based on existing data

BI Study Number 0205-0537

c25002535-01

Proprietary confidential information © 2018 Boehringer Ingelheim International GmbH or one or more of its affiliated companies

Name of company: Boehringer Ingelheim																																								
Name of finished medicinal product: Spiriva® Respimat®																																								
Name of active ingredient: Tiotropium bromide (ATC code R03B B04)																																								
Protocol date: 3 Aug, 2018	Study number: 0205-0537	Version/Revision: 1.0	Version/Revision date: 3 Aug, 2018																																					

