9.3.2 Outcomes

9.3.2.1 Primary outcomes

The primary outcome is whether patient has Cardiac arrhythmias on the index date or in the year prior to the index date. Cardiac arrhythmias is defined as having the following readcode in the above mentioned time period:

medcode	readcode	readterm
17597	327..00	ECG: supraventricular arrhythmia
19707	328..00	ECG: ventricular arrhythmia
29371	328Z.00	ECG: ventricular arrhythmia NOS
97780	G559.00	Arrhythmogenic right ventricular cardiomyopathy
6503	G57..11	Cardiac arrhythmias
426	G577.00	Sinus arrhythmia
31690	G57yA00	Re-entry ventricular arrhythmia
53893	Gyu5a00	[X]Other specified cardiac arrhythmias
26670	2432.00	O/E - pulse irregularly irreg.
18746	662S.00	Atrial fibrillation monitoring
45773	6A9..00	Atrial fibrillation annual review

Protocol for non-interventional studies based on existing data

BI Study Number 0205-0537

c25002535-01

Proprietary confidential information © 2018 Boehringer Ingelheim International GmbH or one or more of its affiliated companies

9479	7936A00	Implant intravenous pacemaker for atrial fibrillation
92361	793M000	Perc translum ablat pulmon vein to lft atrium conduct system
105554	8CMW200	Atrial fibrillation care pathway
57832	9Os..00	Atrial fibrillation monitoring administration
90187	9Os0.00	Atrial fibrillation monitoring first letter
90188	9Os1.00	Atrial fibrillation monitoring second letter
90189	9Os2.00	Atrial fibrillation monitoring third letter
90190	9Os3.00	Atrial fibrillation monitoring verbal invite
90191	9Os4.00	Atrial fibrillation monitoring telephone invite
63350	9hF..00	Exception reporting: atrial fibrillation quality indicators
39114	9hF1.00	Excepted from atrial fibrillation qual indic: Inform dissent
2212	G573.00	Atrial fibrillation and flutter
1664	G573000	Atrial fibrillation
35127	G573300	Non-rheumatic atrial fibrillation
96277	G573400	Permanent atrial fibrillation
96076	G573500	Persistent atrial fibrillation
23437	G573z00	Atrial fibrillation and flutter NOS

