9.9 LIMITATIONS OF THE RESEARCH METHODS

The main analysis will exclude patients with other respiratory disease (e.g., COPD). This will exclude asthma-COPD overlap patients and some other patients and the results may not be representative to all asthma patients. However, Spiriva has both asthma and COPD indications. Therefore, for asthma-COPD overlap patients, the reason for initiating Spiriva Respimat can be unclear in existing data. Since the primary objective is to describe the characteristics of asthma patients prior to the initiation of Spiriva Respimat for the treatment of Asthma, it would be reasonable to exclude asthma-COPD overlap patients,

This study is based on existing data. It is possible that misclassification may happen for the measurement of comorbidities. However, we will use all the available data before the index date to minimize the possibility of misclassification.

Some covariates such as smoking status, alcohol use, BMI, pulmonary function, and eosinophil count may not be well recorded in CPRD. In the analyses we will present missing data as a separate category.

Some information may be recorded very infrequently or not at all in CPRD, e.g., number of people in a household, over-the-counter medication use, prescriptions in secondary care. These variables will not be assessed in this study.

The CPRD only includes patient data captured from general practitioners. Although some information about patient contacts with secondary care could be manually entered into the patient record, details about these specialty visits and hospital admissions (including dates, diagnoses, tests performed, length of stay) may be incomplete.

The CPRD may not be representative of all practices in the UK based on geography and size. There are certain patient groups that are missing from primary care records, such as prisoners, private patients, some residential homes and the homeless. Thus, selection bias cannot be ruled out. However, studies suggested that CPRD patients are broadly representative of the UK population in terms of age and sex. Patients are also comparable to the UK census in

terms of ethnicity, and comparable to the Health Survey for England for body mass index distribution in most patient subgroups.

The HES APC data and HES A&E data only have data for patients from England.

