5.1 Does the protocol describe how the study exposure is defined and measured? (e.g. operational details for defining and categorising exposure, measurement of dose and duration of drug exposure)				9.3.1
5.2 Does the protocol address the validity of the exposure measurement? (e.g. precision, accuracy, use of validation sub-study)				N/A

Protocol for non-interventional studies based on existing data

BI Study Number 0205-0537

c25002535-01

Proprietary confidential information © 2018 Boehringer Ingelheim International GmbH or one or more of its affiliated companies

Section 5: Exposure definition and measurement	Yes	No	N/A	Section Number
5.3 Is exposure classified according to time windows? (e.g. current user, former user, non-use)				N/A
5.4 Is exposure classified based on biological mechanism of action and taking into account the pharmacokinetics and pharmacodynamics of the drug?				N/A

Comments:

--

Section 6: Outcome definition and measurement	Yes	No	N/A	Section Number
6.1 Does the protocol specify the primary and secondary (if applicable) outcome(s) to be investigated?				9.3.2
6.2 Does the protocol describe how the outcomes are defined and measured?				9.3.2
6.3 Does the protocol address the validity of outcome measurement? (e.g. precision, accuracy, sensitivity, specificity, positive predictive value, prospective or retrospective ascertainment, use of validation sub-study)				N/A
6.4 Does the protocol describe specific endpoints relevant for Health Technology Assessment? (e.g. HRQoL, QALYs, DALYS, health care services utilisation, burden of disease, disease management)				N/A

Comments:

--

Section 7: Bias	Yes	No	N/A	Section Number

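### The primary arrhythmia outcome can be met by a sinus arrhythmia code or an irregular-pulse examination code alone, which can overstate prevalence by an amount the protocol does not let one estimate

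*Protocol*

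**What the plan says.** Section 9.3.2.1 states: "The primary outcome is whether patient has Cardiac arrhythmias on the index date or in the year prior to the index date". It then sets the scoring rule: "Cardiac arrhythmias is defined as having the following readcode in the above mentioned time period". The table that follows has 28 codes. No second code, ECG confirmation or treatment is asked for.

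Two entries matter here:
- medcode 426 (Read code G577.00), "Sinus arrhythmia"
- medcode 26670 (Read code 2432.00), "O/E - pulse irregularly irreg", where O/E stands for on examination.

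The abstract (Variables) words the same outcome as a diagnosis: "The outcome is whether a patient has a cardiac arrhythmias diagnosis on the index date or in the year prior to the index date".

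Section 9.7.1 tabulates the outcomes along with the covariates. It compares Spiriva Respimat with each other group by ASD and treats 10% or more as meaningful. It describes no analysis with a narrower code list. Section 9.8 says the protocol will be strictly followed and that changes go through amendments, so the list is fixed here and not left to a later document.

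**The concern.** A binary outcome scored on any one code is only as specific as its least specific code. An incidental entry of sinus arrhythmia gives the same outcome value as permanent atrial fibrillation. So does an irregular pulse noted at a consultation and followed by a normal ECG, because nothing in section 9.3.2.1 lets later evidence cancel the code.

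The primary objective is descriptive, so the prevalence among new Spiriva Respimat users is itself a result, and false positives raise it. For the secondary objective, the ASD on this outcome is part of the evidence on channeling. False positives can shift that ASD if the two codes are used at different rates across groups, and to a lesser extent even if they are used at the same rate.

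**Working it through.** **1. Is the effect blocked elsewhere in the protocol?**
- Section 9.9 concedes: "It is possible that misclassification may happen for the measurement of comorbidities". Its remedy is to use all data before the index date. More data can recover missed cases but cannot remove a false positive.
- Annex 2, checklist item 6.3 on the validity of outcome measurement, is ticked Yes, but its section number is given as N/A.
- Annex 3 separates specific from non-specific asthma codes. The arrhythmia list has no such split. (Section 9.2 does not put the asthma split to use either, so this shows only that the distinction was known.)
- Section 9.7.1 has no with-and-without comparison.

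Nothing removes or tests these entries.

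**2. Effect on prevalence (assumed shares).** The document contains no figure that depends on this point, so there is none to reproduce. Inputs: n = 935 in the Spiriva group (section 9.5); a coded prevalence of 5%, which is one of the columns of Table 1; and an assumed share f of coded patients who qualify only through the two codes. Strict prevalence = 5% × (1 − f). Intervals are Wilson 95% intervals, a method that reproduces Table 1 to within about 0.1 point.

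| f | Strict prevalence | Patients | 95% CI |
|---|---|---|---|
| 0 | 5.00% | 47 | 3.8–6.6% |
| 5% | 4.75% | 44 | 3.5–6.3% |
| 10% | 4.50% | 42 | 3.3–6.0% |
| 20% | 4.00% | 37 | 2.9–5.4% |
| 30% | 3.50% | 33 | 2.5–4.9% |

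Only at the top of this assumed range does the strict estimate (3.5%) fall below the lower limit of the coded one (3.8%).

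**3. Effect on the ASD (assumed prevalences).** ASD = |p1 − p2| / √{[p1(1 − p1) + p2(1 − p2)] / 2}.

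Worked case, 5% v 3%: √[(0.0475 + 0.0291)/2] = 0.1957, and 0.02/0.1957 = 10.2%.

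| True prevalences (Spiriva v comparator) | True ASD | Added by the two codes (percentage points) | Coded prevalences | Coded ASD |
|---|---|---|---|---|
| 5% v 3% | 10.2% | 0.2 / 0.2 | 5.2% v 3.2% | 9.98% |
| 5% v 3% | 10.2% | 0.5 / 0.5 | 5.5% v 3.5% | 9.7% |
| 5% v 3% | 10.2% | 0.1 / 0.3 | 5.1% v 3.3% | 9.0% |
| 5% v 3% | 10.2% | 0.1 / 0.5 | 5.1% v 3.5% | 7.9% |
| 5% v 3% | 10.2% | 0.3 / 0.1 | 5.3% v 3.1% | 11.0% |
| 5% v 3% | 10.2% | 0.5 / 0.1 | 5.5% v 3.1% | 11.9% |
| 6% v 3% | 14.5% | 0.1 / 0.5 | 6.1% v 3.5% | 12.2% |
| 7% v 4% | 13.2% | 0.5 / 0.5 | 7.5% v 4.5% | 12.7% |

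At 4% v 3% the ASD is 5.4%, below the rule before any false positive is added.

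At these prevalences equal additions shrink the ASD slightly. Unequal additions move it down or up, depending on which group receives more. The rule is crossed only in the rows that start at 10.2%.

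**The case against.** **The word diagnosis.** A reader might infer that the abstract's "whether a patient has a cardiac arrhythmias diagnosis on the index date" contradicts a list containing an examination sign. The document does not support that firmly. Section 9.2 defines an asthma diagnosis as at least one medcode and a COPD diagnosis as at least one Read code, so in this protocol a diagnosis means the presence of a listed code. The tension is one of wording.

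**The coding hierarchy.** The sinus arrhythmia code G577.00 shares its G57 stem with the general cardiac arrhythmias entry G57..11 on the same list, so including it follows the coding system. That explains the choice. It does not make the code specific, although the judgment that sinus arrhythmia is usually benign comes from general medical knowledge and not from the protocol.

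**A broad list may be deliberate.** The heart failure list in section 9.3.2.2 is just as inclusive, with suspected disease and screening entries. An irregularly irregular pulse can be true atrial fibrillation, and a recorded irregular pulse may be relevant to what a prescriber knew. This stands for medcode 26670, and it is why that code should be reported both ways and not simply deleted.

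**Requiring a second code.** Counting 26670 only alongside another listed code would not help. If the other code lies within the outcome year, the patient already scores. If it is older, the rule brings an open-ended look-back into a one-year outcome.

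**Conclusion.** The point holds at low severity. As written, a usually normal rhythm variant or an unconfirmed sign is enough to meet the primary outcome, and nothing in the protocol removes or measures this. The prevalence can be overstated. The amount cannot be found from the protocol, and the share of patients qualifying only through these codes could be zero.

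A reader might go further and infer that the two codes dilute a real contrast below the 10% rule. That is not supported. The direction depends on which group carries more of these codes, which the protocol does not show. Sinus arrhythmia entries may be more common in younger patients, but a pulse sign that tracks atrial fibrillation would not follow that pattern. A crossing also needs a true ASD close to 10%: the 5% v 3% example starts at 10.2% and is easily tipped, whereas 6% v 3% and 7% v 4% stay above the rule in the cases shown. All prevalences and added percentages in the ASD table, and the shares f, are assumptions.

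**What to change.** 1. Remove medcode 426 from the list in section 9.3.2.1.
2. Report the primary outcome and its ASDs with and without medcode 26670. Keep the window of the index date and the year before it, and add no longer look-back.
3. Give, by treatment group, the number of patients who would qualify only through 426 or 26670. This count shows whether the matter is trivial or material.

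The cost is an edit to the code list by amendment, one extra table row and a count. The downside is that the few true cases coded only as sinus arrhythmia are lost.

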9.3.2.2 Secondary outcomes

The secondary outcome is whether patient has Cardiac failure on the index date or in the year prior to the index date. Cardiac failure is defined as having the following readcode in the above mentioned time period:

medcode	readcode	readterm
15058	14A6.00	H/O: heart failure
46912	14AM.00	H/O: Heart failure in last year
21235	1J60.00	Suspected heart failure
9913	1O1..00	Heart failure confirmed
46672	388D.00	New York Heart Assoc classification heart failure symptoms
106198	661M500	Heart failure self-management plan agreed
83502	662p.00	Heart failure 6 month review
12366	662T.00	Congestive heart failure monitoring
30779	662W.00	Heart failure annual review
95835	679X.00	Heart failure education
60099	67D4.00	Heart failure information given to patient
46636	68B6.00	Heart failure screen
105542	8CeC.00	Preferred place of care for next exacerbation heart failure
32945	8CL3.00	Heart failure care plan discussed with patient
103732	8CMK.00	Has heart failure management plan
106008	8CMW800	Heart failure clinical pathway
32898	8H2S.00	Admit heart failure emergency
17851	8HBE.00	Heart failure follow-up
91288	8Hg8.00	Discharge from practice nurse heart failure clinic
102585	8HgD.00	Discharge from heart failure nurse service
26115	8HHb.00	Referral to heart failure nurse
70619	8HHz.00	Referral to heart failure exercise programme

Protocol for non-interventional studies based on existing data

BI Study Number 0205-0537

c25002535-01

Proprietary confidential information © 2018 Boehringer Ingelheim International GmbH or one or more of its affiliated companies

71235	8Hk0.00	Referred to heart failure education group
48897	8HTL.00	Referral to heart failure clinic
106894	8IE1.00	Referral to heart failure exercise programme declined
90935	9hH..00	Exception reporting: heart failure quality indicators
30749	9hH0.00	Excepted heart failure quality indicators: Patient unsuitabl
64062	9hH1.00	Excepted heart failure quality indicators: Informed dissent
106545	9m5..00	High risk of heart failure screening invitation
12627	9N0k.00	Seen in heart failure clinic
19002	9N2p.00	Seen by community heart failure nurse
95021	9N4s.00	Did not attend practice nurse heart failure clinic
83481	9N4w.00	Did not attend heart failure clinic
69062	9N6T.00	Referred by heart failure nurse specialist
32911	9Or..00	Heart failure monitoring administration
19380	9Or0.00	Heart failure review completed
90193	9Or1.00	Heart failure monitoring telephone invite
90192	9Or2.00	Heart failure monitoring verbal invite
72965	9Or3.00	Heart failure monitoring first letter
72386	9Or4.00	Heart failure monitoring second letter
89650	9Or5.00	Heart failure monitoring third letter
21837	G232.00	Hypertensive heart&renal dis wth (congestive) heart failure
28684	G233.00	Hypertensive heart and renal disease with renal failure
57987	G234.00	Hyperten heart&renal dis+both(congestv)heart and renal fail
2062	G58..00	Heart failure
1223	G58..11	Cardiac failure
398	G580.00	Congestive heart failure
2906	G580.11	Congestive cardiac failure
10079	G580.12	Right heart failure
10154	G580.13	Right ventricular failure
9524	G580.14	Biventricular failure
23707	G580000	Acute congestive heart failure
32671	G580100	Chronic congestive heart failure
27884	G580200	Decompensated cardiac failure
11424	G580300	Compensated cardiac failure
94870	G580400	Congestive heart failure due to valvular disease
884	G581.00	Left ventricular failure
23481	G581.11	Asthma - cardiac
43618	G581.12	Pulmonary oedema - acute
5942	G581.13	Impaired left ventricular function
5255	G581000	Acute left ventricular failure
27964	G582.00	Acute heart failure
101138	G583.00	Heart failure with normal ejection fraction
101137	G583.11	HFNEF - heart failure with normal ejection fraction
106897	G583.12	Heart failure with preserved ejection fraction
104275	G584.00	Right ventricular failure
4024	G58z.00	Heart failure NOS
12590	G58z.11	Weak heart

Protocol for non-interventional studies based on existing data

BI Study Number 0205-0537

c25002535-01

Proprietary confidential information © 2018 Boehringer Ingelheim International GmbH or one or more of its affiliated companies

17278	G58z.12	Cardiac failure NOS
96799	G5y4z00	Post cardiac operation heart failure NOS
8966	G5yy900	Left ventricular systolic dysfunction
12550	G5yyA00	Left ventricular diastolic dysfunction
104876	G5yyB00	Right ventricular diastolic dysfunction
104333	G5yyC00	Diastolic dysfunction
20822	Q48y100	Congenital cardiac failure
66306	SP11111	Heart failure as a complication of care
26242	ZRad.00	New York Heart Assoc classification heart failure symptoms

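### Four of the 77 codes that each suffice for the secondary outcome, cardiac failure, do not by their printed terms record cardiac failure as present (minor)

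*Protocol*

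**What the plan says.** The abstract (section 4, Variables) states: "The secondary outcome is whether a patient has a cardiac failure diagnosis on the index date", or in the year before it. Section 9.3.2.2 uses the same window, asks whether the patient has cardiac failure, and gives the rule: "Cardiac failure is defined as having the following readcode in the above mentioned time period". A table of 77 Read codes follows. The section sets no minimum number of codes, no confirmation step and no ranking of codes.

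The table includes these entries:

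- 1J60.00, "Suspected heart failure", followed directly by 1O1..00, "Heart failure confirmed"
- 68B6.00, "Heart failure screen"
- 9m5..00, "High risk of heart failure screening invitation"
- G233.00, "Hypertensive heart and renal disease with renal failure", which stands between G232.00, "Hypertensive heart&renal dis wth (congestive) heart failure", and G234.00, whose term names both heart failure and renal failure

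Under section 9.7.1 the outcome is tabulated as a count and percentage in each treatment group. Spiriva Respimat is compared with each other group by ASD, and 10% or more is treated as meaningful. Section 9.9 accepts that comorbidities may be misclassified; its stated mitigation is to use all data available before the index date.

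**The concern.** The outcome is meant to say who has cardiac failure, but four of the sufficient codes record something else: a suspicion, a test with no result stated, an invitation sent to someone at risk, and a hypertensive heart and renal disease in which the failure named is renal. A patient whose only listed code in the window is one of these would be reported as having cardiac failure.

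This is the protocol's only named secondary outcome. In a descriptive study the reported percentage is itself the result. The ASD built on it is meant to show channeling, and section 7 says the results may guide the choice of propensity score variables in future studies.

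**Working it through.** **Step 1. Size of the list.** The 9.3.2.2 table has 37 codes from 14A6.00 to 9Or1.00 and 40 from 9Or2.00 to ZRad.00. 37 + 40 = 77. Without the four codes, 77 - 4 = 73.

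**Step 2. Is one code enough?** The rule asks only that a listed code be present. Section 9.2 says at least one code for asthma and for COPD; 9.3.2.2 does not use those words. With no count or confirmation rule stated, one code is still the plain reading.

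**Step 3. The four terms, read against the list itself.**

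- 1J60.00: the next row is a code for confirmed heart failure. The list therefore separates suspicion from confirmation and then counts both.
- 68B6.00: a screening activity, with no result in the term.
- 9m5..00: an invitation to a person at risk, which precedes any finding.
- G233.00: the term names heart disease but not heart failure. Its two neighbours differ from it by naming heart failure.

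**Step 4. Does anything elsewhere repair this?** No other section restricts or validates these codes. Using all data before the index date (9.9) may help to find missed cases. It cannot remove a false positive created by a listed code, and this outcome is in any case confined to one year.

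**Step 5. Illustration of size.** The protocol gives neither the prevalence of cardiac failure nor the frequency of these codes, so there is no planned figure to reproduce. From the protocol: n = 935 in the Spiriva group (9.5) and the 10% ASD threshold (9.7.1). Assumed: true prevalence 1%, all true cases captured by other codes, and k extra patients who are all false.

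True cases: 0.01 × 935 = 9.35.

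Reported percentage = (9.35 + k)/935. Share of counted patients who are true cases = 9.35/(9.35 + k).

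| k | Reported | Share true |
|---|---|---|
| 1 | 10.35/935 = 1.11% | 90% |
| 5 | 14.35/935 = 1.53% | 65% |
| 10 | 19.35/935 = 2.07% | 48% |

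ASD = |p1 - p2| / sqrt{[p1(1 - p1) + p2(1 - p2)]/2}. In the extreme case all the false positives fall in the Spiriva group and the comparator stays at p2 = 1%:

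- k = 5: p1 = 1.53%, ASD = 4.8%
- k = 10: p1 = 2.07%, ASD = 8.7%
- k = 11: p1 = 2.18%, ASD = 9.4%
- k = 12: p1 = 2.28%, ASD = 10.1%

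The number needed to reach 10% depends on the assumed true prevalence: 10 patients at 0.5%, 12 at 1%, 16 at 2% and 23 at 5%. If the codes were equally common in both groups, the percentages would rise but little ASD would be created.

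**The case against.** The strongest reply is that this protocol uses diagnosis as a label for a code list. Section 9.2 defines an asthma diagnosis as at least one listed code, and Annexes 3 and 4 include monitoring letters and administrative entries. A broad list under that word is then the protocol's convention rather than a conflict between abstract and body. This stands as far as the word goes. It does not answer the narrower point, because 9.3.2.2 itself asks whether the patient has cardiac failure.

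A second reply is that the one-year window cuts the other way. A patient whose heart failure was established earlier could have only one of the four codes in the window. Not every such patient is a false positive, and removing the codes would lose any who are true cases. This also stands: the illustration above is an upper case for a given k.

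A third reply is that the study tests no hypothesis and estimates no treatment effect, so an error of unknown size in one row of a long table matters little. That is fair, and it sets the severity.

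A reader might also infer more than the protocol supports:

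- *That much of the list should go.* Referral, non-attendance and information-given codes do not state present failure outright either, but they refer to care for heart failure. Terms such as G58z.11 and G5yyC00 describe the state of the heart. The printed terms alone do not justify removing them.
- *That Annex 3, by splitting asthma codes into specific and non-specific, sets a standard this list fails.* Section 9.2 refers to Annex 3 as a whole and does not say that the two parts are used differently.
- *That G233.00 is double counted with the renal failure covariate in 9.3.3.* The code list for that covariate is not shown.
- *That the arrhythmia list in 9.3.2.1 has a matching fault.* Whether it omits codes cannot be judged without the code dictionary.

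**Conclusion.** The point holds for four named codes. As written, 9.3.2.2 would report as cardiac failure any patient whose only listed code in the window is a suspicion, a screen, a screening invitation or G233.00, and nothing else in the protocol corrects this.

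The size is not known. If the four codes are rare as sole codes, the error is near zero. At an assumed 1% prevalence, a handful would visibly raise the reported percentage, but reaching the ASD threshold would take 12 false positives in the Spiriva group and none in the comparator. A reader might conclude that the channeling comparison is biased. The protocol does not support that, since nothing in it shows that these codes are frequent or unevenly spread between groups. Severity: minor.

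**What to change.** In section 9.3.2.2, remove 1J60.00, 68B6.00, 9m5..00 and G233.00 from the main definition of cardiac failure, leaving 73 codes. If a broad measure is wanted, report the 77-code list as a sensitivity definition labelled as any heart-failure-related code, and give both percentages for each treatment group. The difference between them would show how much the four codes matter.

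The cost is an edit to the code list, a short amendment (section 9.8 requires changes to be documented that way) and a re-run on the in-house data set (9.6). No new data are needed. The downside is a slightly lower count, including the loss of any true case whose only listed code in the one-year window is one of the four; the 77-code sensitivity definition would still count those patients.
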